Title: A Phase 2, Double-blind, Randomized, Placebo-controlled Multicenter Study to Evaluate Efficacy, Safety, and Tolerability of JBT-101 in Systemic Lupus Erythematosus

Study Sponsor: The National Institute of Allergy and Infectious Diseases (NIAID)

INSTRUCTIONS: The site Principal Investigator should print, sign, and date at the indicated location below. A copy should be kept for your records and the original signature page sent. After signature, please return the original of this form by surface mail to:

DAIT Regulatory Management Center (RMC)

Pharmaceutical Product Development (PPD)

[name]

[name]

I confirm that I have read the above protocol in the latest version. I understand it, and I will work according to the principles of Good Clinical Practice (GCP) as described in the United States Code of Federal Regulations (CFR) – 45 CFR part 46 and 21 CFR parts 50, 56, and 312, and in the International Conference on Harmonization (ICH) document *Guidance for Industry: E6 Good Clinical Practice: Consolidated Guidance* dated April 1996. Further, I will conduct the study in keeping with local legal and regulatory requirements.

As the site Principal Investigator, I agree to carry out the study by the criteria written in the protocol and understand that no changes can be made to this protocol without the written permission of the IRB and NIAID.

Site Principal Investigator (Print)

Site Principal Investigator (Signature)

Date

PROTOCOL SYNOPSIS

Title of the Protocol: A Phase 2, Double-blind, Randomized, Placebo-controlled Multicenter Study to Evaluate Efficacy, Safety, and Tolerability of JBT-101 in Systemic Lupus Erythematosus

ACE Protocol Number: ALE09

Protocol Chair(s): [name].

IND Holder: DAIT/NIAID, NIH

Objectives: To evaluate the efficacy, safety, tolerability, and biologic effects of JBT-101. The primary objective is to evaluate effect on inflammatory pain related to active musculoskeletal disease in SLE.

Hypotheses/Estimates: The hypothesis is that JBT-101 will provide clinical efficacy in SLE patients with at least moderate musculoskeletal disease activity by activation of pathways that resolve ongoing, adverse immune responses and inhibit inflammatory cytokine production associated with SLE.

Study Arms: four cohorts:

JBT-101 5 mg q a.m. and JBT-101 5 mg q p.m.

JBT-101 20 mg q a.m. and placebo q p.m.

JBT-101 20 mg q a.m. and JBT-101 20 mg q p.m.

Placebo q a.m. and placebo q p.m.

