- The average half-life ranged from 3.7 to 5.6 hours for single doses.
- There were no effects of the fed state at 20 and 40 mg doses.
- Following JBT-101 administration at 20-40 mg b.i.d. for 7 days in humans, the only observable plasma metabolite of JBT-101 was a glucuronide metabolite [103], which represented 9% of total JBT-101 present in the plasma.

The safety findings in each completed individual clinical trial can be found in detail in the IB for JBT-101. In summary, key safety findings from the two Phase 1 trials (CT-3-01, CPL7075-100-01) and two Phase 2 trials (CPL7075/02/01/001.1, JBT101-SSc-001) are:

- Maximum Tolerated Dose is 180 mg total daily dose
- No deaths and no serious, severe or unexpected AEs related to JBT-101 occurred in any of the studies
- One of 27 (3.7%) JBT-101-treated subjects in the SSc trial (JBT101-SSc-001) withdrew due to a TEAE of moderate dizziness.
- Mild to moderate AEs consistent with CB1/CB2 agonists occurred at higher doses, especially ≥ 150 mg/day total daily dose
- In pooled safety data, TEAEs that occurred in ≥ 5% of 88 JBT-101-treated subjects who received doses within the estimated therapeutic range of ≤ 60 mg total daily dose were dizziness (n = 10, 11%), dry mouth (n = 5, 5.6%), arthralgias (n = 6, 6.8%), GI disturbances (n = 6, 6.8%) and fatigue (n=9, 10.2%). Note that the majority of subjects with GI complaints (6/6), fatigue (8/9) and arthralgias (6/6) were in the SSc trial and all of these symptoms are common in SSc.
- In pooled safety data of all trials (n = 150 total) and all doses of JBT-101, which included 71 subjects who received JBT-101 at doses higher than the estimated therapeutic range, TEAEs that were observed in two or more subjects ≥ 5% of the time included mild dizziness (21.3%), moderate dizziness (10%), mild somnolence (6%), mild nausea (12%), mild dry mouth (8%), and mild fatigue (5.3%) (Table 27 of the Investigator Brochure for JBT-101). These AEs were consistent with CB1/CB2 agonist class effects and showed a dose-response. Most AEs occurred in the highest frequency in subjects who received ≥ 150 mg total daily dose of JBT-101. Adverse events that were reported in ≥ 5% of placebo-treated subjects were headache (5.7%). There were no AEs or laboratory abnormalities that indicated immunosuppression or an increase in rate of infection.

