- The 5 mg q.d. dose has some but more limited effects than 20 mg b.i.d. on biomarkers in the sputum in cystic fibrosis patients, with biologic effects of 20 mg b.i.d. ≥ 20 mg q.d. and > 5 mg q.d. doses
- In a human model of innate immune responses (E. coli- induced cutaneous inflammation) the 5 mg b.i.d. dosing demonstrates the expected mechanism of action by enhancing resolution of inflammation. Some activities such as induction of Specialized Pro-resolving lipid Mediators are less with 5 mg b.i.d. than with 20 mg b.i.d. whereas other activities such as inhibition of neutrophil infiltration in the skin are equal

Since the 5 mg b.i.d. dose does not pose any safety issues, we plan to use 5 mg b.i.d. as the low dose arm. The JBT-101 20 mg dose is expected to provide maximal or near maximal levels of clinical benefit, and the JBT-101 20 mg b.i.d. dose is expected to provide maximal/plateau levels of clinical benefit. Inclusion of the JBT-101 20 mg q.d. and 20 mg

b.i.d. doses is expected to maximize opportunity to detect clinical efficacy, safety signals, evidence of biologic activity, and effects on biomarkers in this study. Finally, the availability of data from three different doses of JBT-101 will facilitate the exploratory modeling of relationships between plasma concentrations of JBT-101 and efficacy outcomes, SAEs, biomarkers of inflammation, and levels of certain SPMs.

The 84 days duration of dosing is supported by findings in 13-week toxicology studies in rats and dogs. This study will provide data on safety, tolerability, plasma concentrations, and clinical efficacy of JBT-101 over a longer exposure than in a shorter study.

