In support of oral administration q.d. or b.i.d. without regard to fed/fasted state, JBT-101 is well absorbed from the gastrointestinal tract and exhibits dose proportional PK at the doses to be tested in this study. Based on PK results in previous clinical trials, Tmax is expected to be between 2.7 to 3.5 hours for the 5 and 20 mg doses in the current trial, which supports the timing of 3 hours post dosing as an estimate of time of maximal plasma concentrations. The average terminal chemical half-life of JBT-101 in subjects who received 10 mg or 20 mg q.d. in previous studies ranges from 3.7 to 4.4 hours and the biologic effects of JBT-101 are longer, which supports q.d. and b.i.d. testing. Doses to be tested in this study have not shown a significant food effect in a prior clinical study, which supports dosing without regard to fed state.

1.6.3 **Rationale for the Control Arm**

Inclusion of a placebo cohort in this study is important to control for variations in disease activity and AEs that occur commonly in SLE as a result of their disease, co-morbid illness and/or adverse effects of prescribed medications. Because of the relatively short duration of the study and maintenance of the subject's existing medications for musculoskeletal disease activity and pain, the inclusion of a placebo cohort does not impose undue risk on these subjects. To limit risk of increasing disease activity in a placebo-controlled trial, patients with a BILAG A in any organ system at Screening or Visit 1 (Day 1) will be excluded, because those individuals should receive a new treatment for that severely active organ system. Subjects will be maintained on their SLE medications from Screening throughout Visit 6 (Day 113), to reduce a risk of disease flare precipitated by discontinuation of medications to meet entry criteria. Stopping rules will limit the risk of AEs due to severe increases in disease activity.

1.6.4 **Rationale for Mechanistic Studies**

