2.3 Exploratory Objectives

The exploratory objectives of this trial are:

- 1. Explore impact of JBT-101 on symptoms of fibromyalgia
- 2. Explore relationships between JBT-101 plasma concentrations and efficacy, SAEs, biomarkers of inflammation, and certain SPMs, including lipoxin A4

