6.3.2 Metabolipidomic Profile

Metabolipidomic profiles will be assessed in plasma at Visit 1 (Day 1) and Visit 2 (Day 15). At Visit 1 (Day 1), metabolipidomic profiles will be assessed before and 2.5 to 3.5 hours after study product is administered. The metabolipidomic profiles will include measurement of certain SPMs, anti-inflammatory eicosanoids, and pro-inflammatory eicosanoids. As possible, the blood samples for metabolipidomic profile testing should be collected at least 2 hours after the last solid meal.

6.3.3 **JBT-101 Plasma Concentrations and Metabolites**

Plasma concentrations of JBT-101 and its metabolites will be measured at Visit 1 (Day 1) and Visit 2 (Day 15). At Visit 1 (Day 1), plasma levels of JBT-101 and metabolites will be measured before and 2.5 to 3.5 hours after study product is administered.

JBT-101 plasma concentrations and metabolites will be measured using validated assays [101]. Collection at 3 hours after dosing should provide concentrations near peak plasma concentrations and first pass metabolites.

6.3.4 **Optional Unspecified Future Studies**

If the subject provides written informed consent, extra serum and leftover specimens derived from blood samples, including serum, plasma, mRNA, whole blood cells, and whole blood cells culture supernatants, will be stored for future unspecified studies related to JBT-101, the immune system, or SLE.

In addition, if appropriate consents are given, peripheral blood mononuclear cell (PBMC) samples for future, unspecified, IRB approved studies related to JBT-101, the immune system, or SLE will be collected at Visit 1 (Day 1) and follow-up visits per Table 3, *Schedule of Events*.

6.3.5 **Blood Draw Prioritization**

The volume of blood to be drawn at a given visit is limited under the following situations:

- Should the subject have been experiencing severe anemia (hemoglobin < 8g/dL) or have poor venous access, the blood draw limit is 30 mL.
- Should the subject have been experiencing moderate-severe anemia (hemoglobin 8-9 g/dL), the blood draw limit is 50 mL.

• In any patient whose clinical condition might be adversely affected by removal of the volumes required for this protocol, for example, patients with significant anemia (as noted above) or compromised cardiac output, investigators should consider further limiting the volume of blood withdrawn for research purposes.

The priority of samples to collect is as follows:

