 - Remind subject to refrain from taking morning dose before Visit 2. Subjects with visits after 2 PM will be instructed to take their morning dose. This is being done to measure trough plasma concentration of JBT-101 at specified visits.

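### Neither planned post-dose concentration alone orders the active arms by daily exposure, and the Visit 2 procedures list no dose times

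*Protocol*

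**What the plan says.** Section 1.6.2 expects safety and efficacy to follow exposure and states that having three doses "will facilitate the exploratory modeling of relationships between plasma concentrations of JBT-101 and efficacy outcomes, SAEs, biomarkers of inflammation" and certain lipid mediators. Section 2.3 lists the matching exploratory objective: "Explore relationships between JBT-101 plasma concentrations and efficacy, SAEs, biomarkers of inflammation, and certain SPMs, including lipoxin A4".

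The regimens are "JBT-101 5 mg q a.m. and JBT-101 5 mg q p.m" (Cohort 1, 10 mg/day), "JBT-101 20 mg q a.m. and placebo q p.m" (Cohort 2, 20 mg/day), and 20 mg both morning and evening (Cohort 3, 40 mg/day). Doses must be at least 8 hours apart (Section 5.2).

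Under Section 6.3.3, drug levels are taken before and 2.5 to 3.5 hours after the first dose at Visit 1, and once at Visit 2. The reminders in Section 6.4.2.1 ask subjects to hold the morning dose before Visit 2, except those with visits after 2 PM, who take it. The reason given is "This is being done to measure trough plasma concentration of JBT-101 at specified visits". Visit 1 procedures require the time of the clinic dose to be recorded. The Visit 2 list (Section 6.4.2.2) has a capsule count but no dose time.

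For 10 or 20 mg q.d., Section 1.6.2 says the average half-life "ranges from 3.7 to 4.4 hours". Section 1.3.4 gives 3.7 to 5.6 hours across single doses. Section 8.3.4 commits only to descriptive summaries of concentration by visit.

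**The concern.** Both sections name plasma concentration as the quantity to be related to outcomes, and neither says which concentration or exposure summary. If the first-dose level is used as it stands, any effect of the second daily 20 mg dose appears as scatter at one concentration. If the Visit 2 level is used, 20 mg q.d. looks like the lowest-exposure active arm in held-dose samples but not in afternoon samples. In either case the exposure-response picture meant to help choose dose and regimen would be distorted.

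The choice of exposure summary can be made later. Dose times that are not collected cannot be recovered later, and without them a Visit 2 level cannot be reliably placed on the concentration-time curve.

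**Working it through.** The protocol states no figure for this modelling, so there is nothing to reproduce.

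**Inputs.** Regimens: Section 3.1, Table 1. Half-life h: 3.7 to 4.4 h (Section 1.6.2), up to 5.6 h (Section 1.3.4). Dose-proportional kinetics: Section 1.6.2. Assumed: linear kinetics, steady state by Day 15, and an a.m.-to-p.m. gap g of 8 to 12 h.

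**First-dose level.** It is proportional to the first dose: 5, 20 and 20 mg, so 1 : 4 : 4. The Cohort 3 to Cohort 2 ratio is 1.0, against a daily-dose ratio of 40/20 = 2.

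**Held-dose Visit 2 sample.** After absorption, a dose D taken t hours earlier contributes D × 2^(−t/h). If the sample is s hours after the p.m. dose, the a.m. dose is s + g hours old. Earlier days add a factor common to all arms, which cancels. Hence:

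- Cohort 1 / Cohort 2 = 5 × [2^(−s/h) + 2^(−(s+g)/h)] / [20 × 2^(−(s+g)/h)] = ¼ × (1 + 2^(g/h))
- Cohort 3 / Cohort 2 = 1 + 2^(g/h)

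| h (hours) | C1/C2, g = 8 | C1/C2, g = 12 | C3/C2, g = 12 |
|---|---|---|---|
| 3.7 | ¼(1 + 4.48) = 1.37 | ¼(1 + 9.47) = 2.62 | 10.47 |
| 4.0 | ¼(1 + 4.00) = 1.25 | ¼(1 + 8.00) = 2.25 | 9.00 |
| 4.4 | ¼(1 + 3.53) = 1.13 | ¼(1 + 6.62) = 1.91 | 7.62 |
| 5.6 | ¼(1 + 2.69) = 0.92 | ¼(1 + 4.42) = 1.35 | 5.42 |

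The daily-dose ratios are 0.5 for C1/C2 and 2 for C3/C2. A one-compartment model with oral absorption and a 3 h peak gives nearly the same C1/C2 at g = 12: 2.58, 2.23, 1.90 and 1.35. The order reverses when 2^(g/h) > 3, that is g > 1.585h: 7.0 h at h = 4.4, but 8.9 h at h = 5.6.

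**Afternoon Visit 2 sample.** Assume the a.m. dose was taken 7 h earlier and the p.m. dose 19 h earlier. Then C2/C1 = 4 / (1 + 2^(−12/h)), which is 4/1.106 = 3.62 at 3.7 h and 4/1.151 = 3.48 at 4.4 h (one-compartment model: 3.59 and 3.46). C3/C2 is only 1.12 to 1.16 in that model. So the order of Cohorts 1 and 2 at Visit 2 depends on the appointment time.

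**Timing within a sample type.** A held-dose sample taken x hours later is lower by 2^(−x/h). At h = 4.0, a 4-hour delay halves it.

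**What the two samples give together.** A simulation used 25 subjects per active arm, h = 4.4, g = 12, held-dose samples, between-subject SDs of 0.2 to 0.5 on the log scale for clearance and volume, and 15% assay error. Mean rank correlation with true daily AUC was 0.68 to 0.71 for the first-dose level and 0.68 to 0.75 for the trough. It was 0.98 for a compartmental fit to both samples with known regimen and times. The 0.98 is optimistic, because the fit used the true model form and typical parameters. Daily dose alone gave 0.76 to 0.94.

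**SAE counts.** With about 25 per arm, 75 subjects receive JBT-101. Assumed all-cause rates of 1%, 5% and 10% give 75 × 0.01 = 0.75, 75 × 0.05 = 3.75 and 75 × 0.10 = 7.5 subjects with an SAE. The chance of at least 5 is 0.1%, 32% and 88%.

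**The case against.** **The analysis is exploratory and unspecified.** Section 8.3.4 fixes no model, and Section 8.10 leaves detail to a statistical analysis plan. This largely stands: the choice of metric could properly sit there. It does not cover the missing dose times. The electronic case report form has a study drug administration page (mentioned in Section 7.5.2) whose content is not shown, and it may capture them. If so, only the wording needs to change.

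**A reader might infer that the design cannot rank exposure at all.** It can. The tie is confined to the first-dose level and the reversal to the trough. The trough separates Cohorts 2 and 3 by 7.6 to 10.5 times at a 12-hour gap, and the first-dose level separates Cohort 1 from both by 4 times. Section 8.3.2.2 also plans a separate dose-response analysis using the assigned dose.

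**Daily AUC is not the right exposure for every outcome.** This stands. Section 1.3.1 expresses safety margins by peak concentration. Lipid mediators are drawn with the drug level (Section 6.3.2). Three hours after the first dose Cohorts 2 and 3 have had the same 20 mg, so for those outcomes the tie is correct.

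**A reader might infer that SAE modelling is impossible.** The documents do not show this. Section 1.3.4 states "No deaths and no serious, severe or unexpected AEs related to JBT-101 occurred in any of the studies", which concerns related events. It also mentions all-cause SAEs in the cystic fibrosis trial. No all-cause rate in lupus is given.

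**Nor do the documents support swapping SAEs for dizziness, fatigue and dry mouth of any grade.** Section 7.3.1 collects only Grade 2 and above. The pooled figures in Section 1.3.4 are mostly mild (mild dizziness 21.3% against moderate 10%), and the dose-response noted there comes from data that include 71 subjects above the estimated therapeutic range.

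**Conclusion.** The point holds in limited form. Neither post-dose concentration, taken alone, orders the active arms by daily exposure. The first-dose level is expected to be equal under 20 mg q.d. and 20 mg b.i.d. For held-dose samples the trough ranks 5 mg b.i.d. above 20 mg q.d. over the half-life stated for these doses, at every gap checked from 8 to 12 hours. The reversal is lost at an 8-hour gap with a 5.6-hour half-life. The sizes rest on linear kinetics and steady state.

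The after-2-PM exception makes the Visit 2 order depend on appointment time, and the listed Visit 2 procedures do not record what is needed to correct for that. SAEs are likely too few to be informative at 1 to 5%, but that rate is an assumption.

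The objective is exploratory and the primary inference on pain is unaffected. This is a cheap improvement.

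**What to change.** 1. In Section 6.4.2.2, record at Visit 2 the clock times of the last a.m. dose, the last p.m. dose and the pharmacokinetic sample.
2. In Sections 1.6.2 and 2.3, state that for efficacy, safety and later biomarker outcomes the exposure variable is model-derived, for example predicted steady-state AUC0-24 from both samples, the regimen and the recorded times. Keep concurrent concentration for lipid mediators sampled at the same time.
3. Optionally, add related TEAEs of Grade 2 or higher beside SAEs, and note that SAEs may be too few to be informative.

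Cost: one extra case report form entry at one visit and a few lines of text, with no added blood or visits. The downside is reliance on a simple linear pharmacokinetic model.

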4.1 Inclusion Criteria

Individuals who meet ALL of the following criteria at Screening are eligible for enrollment:

- 1. Fulfill the updated ACR 1997 Revised Criteria for the Classification of Systemic Lupus Erythematosus [108]
- 2. ≥ 18 and ≤ 70 years of age at the time the Informed Consent Form is signed
- 3. At least 3 months treatment with an anti-malarial drug such as hydroxychloroquine or a history of intolerance, contraindication, or unwillingness to take an anti-malarial drug
- 4. Meets the SELENA SLEDAI definition of arthritis [109] or moderate arthritis or tendonitis that has not improved over the last month (i.e. BILAG B on the updated BILAG 2004 [110])

- 5. Seven-day average of maximum of daily pain NRS scores ≥ 4 out of 10 during screening with continued reporting of pain NRS scores on at least 67% of days between the Screening visit and randomization.
- 6. Overlap with polymyositis, systemic sclerosis, Sjögren's syndrome, or rheumatoid arthritis is allowed, if, in the site investigator's judgment, the predominant clinical features are those of SLE
- 7. Not expected by the site investigator to require a change in potential disease-modifying treatments for SLE from Screening through Visit 6 (Day 113)
- 8. Willing to not start or stop any NSAIDs or potential disease-modifying medications or supplements for SLE from Screening through Visit 6 (Day 113), unless a change is recommended by the site investigator or other treating physicians
- 9. Willing not to use any legal or illegal cannabinoids, including FDA-approved cannabinoids or cannabinoid-mimic drugs, or any illegal substance of abuse from Screening through Visit 6 (Day 113)
- 10. If a woman of child-bearing potential, willing to use one of the highly effective (failure rate < 1% per year) birth control method from Screening through Visit 6 (Day 113) or for 28 ± 3 days after the last dose of study product (See Appendix A: Reproductive Potential and Effective Methods of Contraception)
- 11. Willing to follow instructions, complete study procedures and attend study visits as required by this protocol

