4.2 Exclusion Criteria

Individuals who meet ANY of the following criteria are not eligible for enrollment:

- 1. Severe or unstable SLE, such as any one of the following:
 - a. A BILAG A score in one or more BILAG domains at Screening
 - b. Treatment with any intraarticular, intravenous, or intramuscular systemic corticosteroids within 14 days of Screening
 - c. Treatment with oral prednisone > 10 mg per day or > 20 mg every other day (or equivalent dose of another corticosteroid) within 14 days of Screening
 - d. Increased dose of systemic corticosteroids in the 14 days prior to Screening
 - e. Treatment with cyclophosphamide or anti-TNFα biologic agents within 3 months before Visit 1 (Day 1)
 - f. Treatment with B cell-depleting monoclonal antibodies (rituximab, Ocrelizumab, anti-CD-22) within 6 months before Visit 1 (Day 1)
 - g. Treatment with methotrexate, mycophenolate, azathioprine, leflunomide, cyclosporine, belimumab, tacrolimus, or any other immunosuppressive agent not included in 1b.-f. above, when the dose of that immunosuppressive agent has increased within 3 months before Visit 1 (Day 1). Concurrent treatment with any of

these medications is allowed as long as the doses have been stable for at least 3 months before Visit 1 (Day 1)

- h. Actively listed on an organ transplantation list or have received an organ transplant other than a corneal transplant
- 2. Significant diseases or conditions other than SLE that may influence response to the study product or safety, such as:
 - a. Active bacterial or viral infection requiring systemic antibiotic or anti-viral treatment within 14 days before Visit 1 (Day 1)
 - b. Acute or chronic hepatitis B or C infection
 - c. Human immunodeficiency infection
 - d. History of active tuberculosis or positive tuberculosis skin or blood test without: 1) completing a course of appropriate treatment; or 2) having received at least one month of appropriate treatment prior to Visit 1 (Day 1) and continuing to receive appropriate treatment during the study
 - e. No elective surgery should be planned from Visit 1 (Day 1) through Visit 6 (Day 113)
 - f. A history of cancer. Except basal cell carcinoma or in situ carcinoma of the cervix treated with apparent success with curative therapy greater than one year before Visit 1 (Day 1)
 - g. Significant heart disease as defined by:

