 - i. Uncontrollable congestive heart failure, unstable angina, unstable atherosclerotic cardiovascular disease, significant arrhythmia requiring chronic therapy, pulmonary arterial hypertension with dyspnea, disability rated as New York heart Association Grade III or higher, severe systemic hypertension or severe peripheral vascular disease
 - ii. Marked baseline prolongation of QT/QTc interval (i.e. repeated demonstration of a QTc interval \geq 450 msec for males and \geq 470 msec for females)
 - iii. History of risk factors for torsade de pointes (e.g., heart failure, hypokalemia)
 - iv. Clinically significant confirmed abnormality, as determined by the site investigator or qualified designee, on 12-lead ECG at Screening
- 3. History of chronic pain requiring treatment with narcotic analgesia for more than 30 days total within 6 months (183 days) of baseline. This does not include self-limited pain associated with identifiable events such as surgery
- 4. Current evidence of alcohol abuse (defined as 4 or more drinks per day on at least 4 days of the week) or history of abuse of illegal and/or legally prescribed drugs such as barbiturates, benzodiazepines, amphetamines, cocaine, or opioids during the 1 year prior to Screening
- 5. Currently pregnant, breast-feeding, or lactating

- 6. Any investigational agent within 30 days or five therapeutic half-lives of that agent whichever is longer, before Visit 1 (Day 1)
- 7. Any of the following values for laboratory tests at Screening:
 - a. A positive pregnancy test (also at Visit 1 (Day 1))
 - b. A newly positive QuantiFERON® blood test for tuberculosis, without: 1) completing a course of appropriate treatment; or 2) having received at least one month of appropriate treatment prior to Visit 1 (Day 1) and continuing to receive appropriate treatment during the study. If the subject has a previous documented positive tuberculosis skin, then this testing does not need to be repeated. If the subject has a documented negative test result within the last year, testing does not need to be repeated, at the discretion of the site investigator
 - c. Hemoglobin < 8 g/dL
 - d. Neutrophils $< 1.0 \times 10^9/L$
 - e. Platelets $< 75 \times 10^9/L$
 - f. eGFR < 50 ml/min according to Cockcroft-Gault equation
 - g. AST, ALT, or alkaline phosphatase > 2.0 x upper limit of normal

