- 8. Any other conditions that, in the opinion of the site investigator, are clinically significant and may put the subject at greater safety risk, influence response to study product, or interfere with study assessments. When in doubt, the site investigator or qualified designee should discuss the situation with the Protocol Chairs.

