5.8 Treatment Discontinuation and Subject Withdrawal

5.8.1 **Interruption of Dosing and Study Treatment Discontinuation**

Interruption of continued dosing in individual subjects may occur for safety reasons and at the discretion of the site investigator, if it is felt that interruption of dosing is in the best interest of the subject. Other than in urgent situations, it is recommended that the site investigator discuss the reasons for interruption of dosing with the Protocol Chairs and DAIT/NIAID prior to interruption. Multiple on-off periods of treatment with study drug are permitted, as necessary in the judgment of the investigator for safety purposes.

Study treatment will be discontinued permanently for any individual subject under the following conditions:

- 1. At any time during the study at the request of the subject or subject's guardian
- 2. If investigators or the DAIT/NIAID Medical Monitor determine(s) that the subject's health, safety, and/or well-being are threatened
- 3. Study treatment will be discontinued for any subject who experiences any of the following:
 - A severe flare by the SELENA SLEDAI Flare Index or a BILAG A in any domain except musculoskeletal
 - Starting a medication that is prohibited during the study (See Table 2 in Section 5.6, *Prohibited Medications*)
 - Increases in doses of methotrexate, mycophenolate, azathioprine, leflunomide, belimumab, cyclosporine, or tacrolimus above stable baseline doses
 - Any Grade 3 or higher AE or SAE that, in the opinion of the blinded site investigator, is at least "possibly related" to study product
 - Pregnancy. (See Section 7.6, *Pregnancy Reporting*)

Abrupt discontinuation of treatment with JBT-101 is not known to cause any harmful effects; therefore, study product will be stopped without tapering or adding additional treatments. All remaining study product will be returned to the study staff.

There will be no dose modification in this study, other than temporary or permanent discontinuation.

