6.4.2.1 Visit 1 (Day 1)

- Verify eligibility criteria
- Patient-reported outcomes, before other interactions with study staff
 - ARCI-M questionnaire (Pre-Dose)
 - Lupus Activity Patient Global Assessment
 - PROMIS-29 Short Form
 - PROMIS Item Bank v2.0 Cognitive Function
 - Fibromyalgia Symptom Scale
- Confirm date of last menstrual period in women of childbearing potential

- Record prior medications
- Vital signs: Height, weight, blood pressure, pulse, respiratory rate, and temperature
- Physical examination
- Physician assessments (all scores will be calculated centrally)
 - o 66/68 joint count
 - SELENA SLEDAI and Flare Index
 - o BILAG 2004
 - Physician's Global Assessment
- AE monitoring
- **Before** study product administration
 - Blood tests
 - Hematology: CBC with differential cell count and platelets
 - Chemistry: Complete metabolic panel, including electrolytes, renal function, and liver function tests
 - CRP
 - Anti-dsDNA antibody titers, C3, and C4 levels
 - o Blood draws for mechanistic studies
 - Whole blood: TruCulture tubes; pro-inflammatory cytokines
 - Plasma: metabolipidomic profile, and JBT-101 plasma concentrations and metabolites; sampled ≥ 2 hours after last solid meal, if possible.
 - RNA: Type 1 IFNα gene signature
 - Serum: future use (if subject provided written consent)
 - PBMC: future use (if subject provided written consent)
- Urine tests before study product administration
 - Urinalysis: microscopic evaluation, and spot protein/creatinine
 - Urine βHCG pregnancy test in women of childbearing potential
- Triplet 12 lead ECGs for medically significant abnormalities and QT/QTc interval prior to study product administration
- Dispense study product according to randomization schedule. Women of child bearing potential must have negative urine βHCG pregnancy test prior to dispensing study product
- Administer study product in clinic and record time of dose

- Observe subject for at least 30 minutes in clinic, until stable in the judgment of the investigator
- 2.5 to 3.5 hours after study product administration
 - ARCI-M questionnaire (Post-Dose)
 - Triplet 12 lead ECGs for QT/QTc interval
 - Blood draws for mechanistic studies
 - Plasma: metabolipidomic profile, and JBT-101 plasma concentrations and metabolites; sampled ≥ 2 hours after last solid meal, if possible
- Reminders:
 - Remind subjects to bring the bottles of study drug with them to their next visit.

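### Section 1.6.3 rules out BILAG A at Screening or Visit 1, but exclusion 1a tests Screening only, so a new grade A on Day 1 is left to judgment

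*Protocol*

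**What the plan says.** Section 1.6.3 (Rationale for the Control Arm) gives the limit on risk from placebo: "patients with a BILAG A in any organ system at Screening or Visit 1 (Day 1) will be excluded". Its reason is that such people need new treatment for the badly affected organ system.

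Section 4.2 turns this into exclusion 1a: "A BILAG A score in one or more BILAG domains at Screening". It stands under an open heading, "Severe or unstable SLE, such as any one of the following". Elsewhere section 4.2 does name the later visit: exclusion 7a reads "A positive pregnancy test (also at Visit 1 (Day 1)".

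Other provisions that bear on a Day 1 grade A are:

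- exclusion 8, a catch-all: "Any other conditions that, in the opinion of the site investigator, are clinically significant";
- inclusion 7: "Not expected by the site investigator to require a change in potential disease-modifying treatments for SLE";
- section 5.8.1, permanent discontinuation for "A severe flare by the SELENA SLEDAI Flare Index or a BILAG A in any domain except musculoskeletal";
- section 6.4.2.1 (Visit 1), which re-verifies eligibility, assesses BILAG, and requires of women of childbearing potential a negative "pregnancy test prior to dispensing study product". It sets no such hold for BILAG.

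**The concern.** The rationale promises a categorical exclusion at two time points and the criterion delivers it at one. Re-verifying eligibility at Visit 1 does not close the gap, because checking 1a as written means looking again at the Screening score.

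Allocation is 1:1:1:1, so one subject in four gets placebo. Section 6.1.5.2 describes grade A as disease likely to need immunosuppressive drugs and/or prednisolone above 20 mg daily, or high-dose anticoagulation. A subject dosed with a Day 1 grade A then has two paths:

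- Remain on study product without that escalation, which is the situation section 1.6.3 says it avoids.
- Escalate. Sustained corticosteroid above the section 5.6 limit, or an increase in a listed immunosuppressant, ends study treatment permanently under section 5.8.1. The subject stays in the mITT population (section 8.2.1), but pain scores after discontinuation are excluded (section 8.3.2.1), so little data is contributed.

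Neither path serves the patient or the trial.

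**Working it through.** No power, sample size or alpha figure is involved, and the plan gives no figure to reproduce. The check sets the provisions side by side and then measures the time left uncovered.

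**Step 1. What each provision does for a grade A that first appears on Day 1**

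| Provision | Applies to a new Day 1 grade A? | Fixed rule or judgment? |
|---|---|---|
| 1.6.3 | Yes, any organ system | Stated as fixed, but in the rationale |
| Exclusion 1a | No, Screening only | Fixed |
| Heading of exclusion 1 | Possibly, as an unlisted example | Judgment |
| Exclusion 8 | Possibly | Judgment |
| Inclusion 7 | Possibly, but section 4.1 applies its criteria at Screening | Judgment |
| 6.4.2.1 eligibility check | Re-checks 1a as written | No BILAG hold |
| 5.8.1 BILAG rule | Non-musculoskeletal only | Fixed, but stops treatment rather than entry |

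A non-musculoskeletal grade A would thus meet a permanent stopping rule on the day treatment starts. A musculoskeletal grade A is excluded by 1.6.3, yet is neither excluded by 1a at Visit 1 nor stopped by the BILAG rule in 5.8.1.

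**Step 2. How much of the Visit 1 BILAG period Screening cannot see**

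Inputs:

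- Gap from Screening to Visit 1: 7 to 42 days (Table 3, note A).
- BILAG look-back: 28 days (section 6.1.5.2).

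Share of the Visit 1 look-back that falls after Screening = min(gap, 28) / 28.

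| Gap (days) | Calculation | Share |
|---|---|---|
| 7 | 7/28 | 25% |
| 14 | 14/28 | 50% |
| 21 | 21/28 | 75% |
| 28 to 42 | 28/28 | 100% |

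The 7-day end requires the BILAG to be done at a later screening visit, which note A permits. If it is done at the initial visit, seven days of pain reporting follow (section 3.1), and randomization must come at least 7 days before Visit 1 (section 6.4.1.1). The gap is then at least 7 + 7 = 14 days, a share of at least 50%.

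This measures exposure time. It does not say how often a new grade A arises, and the protocol gives no rate from which to estimate that.

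**The case against.** The strongest reply is that section 1.6.3 is itself protocol text and is categorical. The heading of exclusion 1 is open and carries no time limit, and eligibility is re-verified at Visit 1. Read together, a Day 1 grade A could be taken as severe disease under exclusion 1, which makes this unclear drafting rather than an open door. That reading is available, but it depends on each site adopting it over the plain words of 1a.

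The comparison with 7a can also be pressed too far. Item 7 is headed as laboratory values at Screening, so 7a needed extra words to escape that limit, and item 1 did not. This weakens the inference about intent; the wording of 1a is unchanged by it.

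On the musculoskeletal case, the same bullet of section 5.8.1 also stops treatment for a severe SELENA SLEDAI flare, with no musculoskeletal exception. Treating a grade A in the usual way would often trigger the prohibited-medication or dose-increase stops. Section 3.1 also says that increased activity should receive standard care, so nobody must go untreated. These points stand and limit the harm. They act on treatment after entry, however, and not on who is dosed.

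Finally, BILAG domain scores are calculated centrally (section 6.2.2). A subject cleared on same-day information could later score A and become an entry violation, open to exclusion from the per protocol population. That is a real cost of tightening 1a.

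**Conclusion.** The concern holds. Section 1.6.3 and exclusion 1a disagree on when BILAG A excludes, and no other section supplies the missing Visit 1 criterion. A subject with a new grade A on Day 1 can be dosed unless an investigator exercises discretion, and the musculoskeletal domain has no fixed BILAG rule before or after dosing.

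The uncovered share of the Visit 1 look-back is 25% to 100%, or at least 50% if BILAG is done at the initial screening visit. These figures rest on the stated 7 to 42 day interval and 28-day look-back. The number of subjects affected is unknown, a careful investigator may exclude them anyway, and the effect on the primary analysis is expected to be small. The point should be corrected because the exclusion is part of the stated justification for giving placebo.

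**What to change.** Amend exclusion 1a so that a BILAG A excludes at Screening or at Visit 1 (Day 1). In section 6.4.2.1, add one step before dispensing: the investigator reviews the BILAG items for a grade A with the information available that day, without waiting for the central score. State there that entry is decided on this check, so that a later central grade A is not by itself an entry violation.

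The cost is one phrase in 1a and a line or two in 6.4.2.1, with no added visit or procedure. Because randomization precedes Visit 1 by at least 7 days, a few randomized subjects may be withdrawn undosed. Section 3.1.1.1 already allows this and does not count them toward the 100, and they fall outside mITT because they receive no dose.

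Deleting the Visit 1 reference from section 1.6.3 would also remove the contradiction, but it would weaken the protocol's own case for the placebo arm, so it is the poorer choice.
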